10.13. Appendix 13: Alternative Measures During Public Emergencies

The alternative study measures described in this section are to be followed during public emergencies, including the coronavirus disease 2019 (COVID-19) pandemic. This appendix applies for the duration of the COVID-19 pandemic globally and will become effective for other public emergencies only upon written notification from Pfizer. **NOTE:** Any deviations from the Schedule of Activities or the protocol (eg, missed or partially completed procedures or assessments) must be reported to the sponsor in a timely manner and will be reported by the sponsor as a protocol deviation.

Procedures which are missed due to disruptions related to a public emergency, including the COVID-19 pandemic, are required to be performed at the next available opportunity, even if outside of a protocol-specified visit window.

Use of these alternative study measures are expected to cease upon the return of business as usual circumstances (including the lifting of any quarantines and travel bans/advisories).

10.13.1. Eligibility

While severe acute respiratory syndrome coronavirus 2 (SARS-CoV2) testing is not mandated for this study, local clinical practice standards for testing should be followed. A de novo patient or a participant originating from B7931005 and B7981015 with >30 days from the first study visit of Study B7981032 and the last dose in the index study should be excluded if he/she has a positive test result for SARS-CoV2 infection, is known to have asymptomatic infection, or is suspected of having SARS-CoV2. De novo patients and participants originating from B7931005 and B7981015 with >30 days from the first study visit of Study B7981032 and the last dose in the index study with active infections are excluded from study participation per Exclusion #17. When the infection resolves, the patient may be considered for re-screening.

For de novo participants and participants originating from Study B7931005 or B7981015 with >30 days between the first visit in Study B7981032 and the last dose in Study B7931005 or B7981015 and who are being considered for enrollment into Study B7981032:

- The participant must be able to perform all Screening and Day 1 procedures per the Schedule of Activities at the study site and/or designated ancillary facility (eg, for audiological evaluations and chest radiographs) in order to determine whether the participant meets eligibility criteria for Study B7981032. This includes collection and resulting of laboratory assessments through the central laboratory vendor.
- The participant must meet eligibility criteria for Study B7981032.
- It must be anticipated that the participant will be able to have the B7981032 Week 2 and Month 1 safety laboratory tests collected/performed at the study site or an alternative clinical laboratory facility according to the windows in Table 5 in Section 10.13.3.1.

• If a participant does not meet the criteria described above, the participant cannot be enrolled in the B7981032 study.

For participants originating from Study B7981015 with ≤30 days between the first visit of Study B7981032 and the last dose in Study B7981015 and who are being considered for enrollment into Study B7981032:

- The participant must meet eligibility criteria for Study B7981032.
- The participant must be able to have safety laboratory tests collected at their final visit in Study B7981015 at the study site or an alternative clinical laboratory facility.
- The participant (if a WOCBP) must be able to have pregnancy testing performed at their final visit in Study B7981015 and the Day 1 visit in B7981032 (if applicable) at the study site, at an alternative clinical laboratory facility, or at the participant's home.
- The participant must be able to have the Day 1 tuberculosis test collected between the time of signing consent/assent for B7981032 and the Week 2 visit (inclusive) at the study site or an alternative clinical laboratory facility.
- It must be anticipated that the participant will be able to have the B7981032 Week 2 and Month 1 safety laboratory tests collected/performed at the study site or an alternative clinical laboratory facility according to the windows in Table 5 in Section 10.13.3.1.
- For participants who are not able to complete all required B7981015 Week 48 or Early Termination procedures and/or B7981032 Day 1 procedures per the respective protocol, these cases must be discussed with the Pfizer B7981032 study team prior to the final visit in Study B7981015 to obtain agreement that the participant may be suitable for entry into B7981032.
- If a participant does not meet the criteria described above, the participant cannot enter the B7981032 study.

10.13.2. Telehealth Visits

In the event that in-clinic study visits cannot be conducted, every effort should be made to follow up on the safety of study participants at scheduled visits per the Schedule of Activities or unscheduled visits. Telehealth visits may be used to continue to assess participant safety and collect data points. Telehealth includes the exchange of healthcare information and services via telecommunication technologies (e.g., audio, video, video-conferencing software) remotely, allowing the participant and the investigator to

communicate on aspects of clinical care, including medical advice, reminders, education, and safety monitoring. The following assessments must be performed during a telehealth visit:

- Review dosing logs and record study intervention(s), including doses taken and any interruptions in intake of study intervention (ie, missed doses) since the last contact, and calculate compliance.
- Review and record any AEs and SAEs since the last contact. Refer to Section 8.3.
- Review and record any new concomitant medications or changes in concomitant medications since the last contact.
- For WOCBP: Review and record contraceptive method and results of pregnancy testing. Confirm that the participant is adhering to the contraception method(s) required in the protocol Appendix 4, Section 10.4.4. Refer to Section 8.2.11 of the protocol and Section 10.13.3.1 of this appendix regarding pregnancy tests and to Section 5.3.1 of this protocol regarding contraception checks.
- For premenarchal female participants: Check for initiation of menarche per Section 8.2.12 of this protocol.
- Collection of updated audiological history (Part 1 in the Audiometry Study Guide Worksheet for Post Day 1 visits) at visits requiring audiological evaluation.
- Body temperature and collection method (eg, oral, tympanic, axillary, or temporal), and pulse rate (measured by study participant/caregiver).
- Administration of the C-SSRS performed by a qualified rater. Per Section 8.2.9.1, if
 there are "yes" answers on items 4 or 5 of the suicidal ideation section or on any question
 in the suicidal behavior section of the C-SSRS, the participant will be discontinued from
 the study and referred to a mental health professional for appropriate evaluation and
 treatment.
- **NOTE:** If the investigator determines that additional evaluation is warranted based on the information collected during the remote visit described above, follow-up is required to be performed, with results submitted to and reviewed by the investigator prior to shipping study intervention to the participant.

Study participants must be reminded to promptly notify site staff about any change in their health status.

10.13.3. Alternative Facilities for Safety Assessments

10.13.3.1. Laboratory Testing

With the exceptions noted in Section 10.13.1 of this appendix for Screening and Day 1, if a study participant is unable to visit the site for protocol-specified safety laboratory

evaluations, testing may be conducted at a local laboratory if permitted by local regulations. The local laboratory may be a standalone institution or within a hospital. Collection of blood and urine samples may also be performed at the participant's home per Section 10.13.5 of this appendix. The following safety laboratory evaluations may be performed at a local laboratory or in the participant's home:

- Hematology
- Serum chemistry
- Lipid panel (for visits on or before Month 36)
- Urinalysis (for visits after Month 36, urinalysis will be performed only if considered clinically indicated by the investigator)
- Pregnancy testing (for WOCBP)
- Day 1 and annual tuberculosis testing
- Refer to the Schedule of Activities for visits at which these tests are required and to Appendix 2 for additional details regarding these tests.

If it is not possible for the participant to have the above tests completed within the visit window specified in the Schedule of Activities, an extended window may be allowed to collect samples for these laboratory tests, provided that the investigator has performed the remote visit as described above, assessed each case, and determined that it would not increase risk to a participant. The extended windows for laboratory sample collection for each study visit are noted in Table 5. These windows apply only to laboratory samples collected during interruptions due to public emergencies, including the COVID-19 pandemic, based upon written notification from Pfizer. If the laboratory samples are not collected within the specified extended window for the visit, the participant must temporarily withhold study intervention until the required laboratory samples can be collected.

If a local laboratory is used, qualified study site personnel must order, receive, and review results. Site staff must collect the local laboratory reference ranges and certifications/ accreditations for filing at the site. Laboratory test results are to be provided to the site staff as soon as possible and must be received and reviewed by the investigator within 14 days after they are collected in order to determine eligibility to continue dosing. In addition, laboratory test results from the previous visit must be available and reviewed by the investigator prior to shipping study intervention at the current visit. The local laboratory reports must be filed in the participant's source documents/medical records. Relevant data from the local laboratory report must be recorded on the CRF.

Special attention should be paid to ensure that laboratory results are checked against the Guidelines for Participant Safety Monitoring and Discontinuation in Appendix 8 and that required follow-up is performed as applicable.

If a participant requiring pregnancy testing cannot visit a local laboratory for pregnancy testing, a home urine pregnancy testing kit with a sensitivity of at least 25 IU/mL may be used by the participant to perform the test at home, if compliant with local regulatory requirements. Urine pregnancy test results may be collected based on information provided by the participant (or their legally authorized representative, if appropriate) during the remote visit. The urine pregnancy test result must be available prior to dispensing or shipping study intervention to a participant. The pregnancy test outcome must be documented in the participant's source documents/medical records and relevant data recorded on the CRF. Confirm that the participant is adhering to the contraception method(s) required in the protocol.

NOTE: Pregnancy testing (for WOCBP) between scheduled study visits and study site contact with participants to obtain pregnancy test results is required to continue as outlined in the Schedule of Activities and Section 8.2.11 of the protocol.

Table 5. Windows for Remote Visits and Laboratory Sample Collections if Required due to Public Emergencies, Including the COVID-19 Pandemic

Visit (Day in Study)	Remote Visit Window	Lab Collection Window
	(Day in Study) ^a	(Day in Study) ^b
Week 2 (Day 15)	±3 days (Day 12-18)	±3 days (Day 12-18)
Month 1 (Day 31)	±3 days (Day 28-34)	-3 / +30 days (Day 28-61)
Month 3 (Day 91)	±7 days (Day 84-98)	-14 / +30 days (Day 77-121)
Month 6 (Day 181)	±7 days (Day 174-188)	-14 / +30 days (Day 167-211)
Month 9 (Day 271)	±7 days (Day 264-278)	-14 / +30 days (Day 257-301)
Month 12 (Day 361)	±7 days (Day 354-368)	-14 / +30 days (Day 347-391)
Month 15 (Day 451)	±7 days (Day 444-458)	-14 / +30 days (Day 437-481)
Month 18 (Day 541)	±7 days (Day 534-548)	-14 / +30 days (Day 527-571)
Month 21 (Day 631)	±7 days (Day 624-638)	-14 / +30 days (Day 617-661)
Month 24 (Day 721)	±7 days (Day 714-728)	-14 / +30 days (Day 707-751)
Month 28 (Day 841)	±7 days (Day 834-848)	-14 / +30 days (Day 827-871)
Month 32 (Day 961)	±7 days (Day 954-968)	-14 / +30 days (Day 947-991)
Month 36 (Day 1081)	±7 days (Day 1074-1088)	-14 / +30 days (Day 1067-1111)
Month 40 (Day 1201)	±7 days (Day 1194-1208)	-14 / +30 days (Day 1187-1231)
Month 44 (Day 1321)	±7 days (Day 1314-1328)	-14 / +30 days (Day 1307-1351)
Month 48 (Day 1441)	±7 days (Day 1434-1448)	-14 / +30 days (Day 1427-1471)
Month 52 (Day 1561)	±7 days (Day 1554-1568)	-14 / +30 days (Day 1547-1591)
Month 56 (Day 1681)	±7 days (Day 1674-1688)	-14 / +30 days (Day 1667-1711)
Month 60 (Day 1801)	±7 days (Day 1794-1808)	-14 / +30 days (Day 1787-1831)

a. These are the same as the windows in the protocol Schedule of Activities (Section 1.3.2).

b. Laboratory results must be received and reviewed by the investigator within 14 days after they are collected to determine eligibility to continue dosing. In addition, laboratory test results from the previous visit must be available and reviewed by the investigator prior to shipping study intervention at the current visit.

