Pregnancy test	X	X	X	X	X	X	X	X	X	X	For WOCBP only. Monthly urine pregnancy tests will be performed by the participant between scheduled study visits starting after the Month 1 visit through the Month 24 visit. The pregnancy testing between visits may occur outside of the study site. Site personnel will contact participants (or their legally authorized representative, if appropriate) via telephone between study visits to obtain monthly pregnancy test result and ensure this contact and the result of the pregnancy test are recorded in participant source documentation and CRF. Section 8.2.11, Appendix 2, Appendix 4

Procedure]	Interv	ention	Perio	d (Mor	iths)			Notes
Visit	Week 2	1	3	6	9	12	15	18	21	24	
HBVDNA (applicable countries)			X	X	X	X	X	X	X	X	For de novo participants and participants originating from Study B7931005 or B7981015 with >30 days between the first visit of Study B7981032 and the last dose in the index study, testing will be dependent on the screening results from Study B7981032. For participants originating from Study B7981015 with ≤30 days between the first visit of Study B7981032 and the last dose in the index study, testing will be dependent on screenings result from the index study. See Appendix 7 for Japan specific requirements. Section 8.2.8.5, Appendix 6
Annual tuberculosis testing/chest radiograph						X				Х	Section 8.2.8.1, Section 8.2.8.1.2, Appendix 2
FACS-TBNK samples collected for possible reflex testing	X	X	X	X	X		X	X	X		Appendix 2
Pharmacodynamic	s markers										
FACS-TBNK						X				X	Section 8.6
Immunoglobulins (IgA, IgG, IgM)						X				X	Section 8.6

Procedure]	Interv	ention	Perio	d (Mor	nths)			Notes
Visit	Week 2	1	3	6	9	12	15	18	21	24	
Trial treatment					ı		1				
Study intervention dispensing	X	X	X	X	X	X	X	X	X	X	At the Week 2 visit, the participant will return the package containing the study intervention which was dispensed at the Day 1 visit for accountability. The Day 1 package will then be returned to the participant for administration and dispensing at the Week 2 visit. Section 6.2
Study intervention administration	X	X	X	X	X	X	X	X	X	X	Section 6.1
Study intervention accountability and compliance	X	X	X	X	X	X	X	X	X	X	Section 6.2, Section 6.4
Clinical assessment	S										

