Study intervention dispensing	X	X	X	Study intervention will only be dispensed and administered at the Month 36 visit for participants continuing to TP2.
Study intervention administration	X	X	X	Study intervention will only be dispensed and administered at the Month 36 visit for participants continuing to TP2. Section 6.1
Study intervention accountability and compliance	X	X	X	Section 6.2, Section 6.4
Clinical assessments				
SALT	X	X	X	For participants with known androgenetic alopecia, this includes a separate assessment of scalp hair loss due to androgenetic alopecia at the final on-therapy visit for each treatment period (ie, at Month 36 or Early Termination in TP1, and at Month 60, the last on-therapy visit, or Early Termination in TP2). Section 8.1.2.1

Procedure	Interven	tion Perio	d (Months)	Notes
Visit	28	32	36	
EBA and ELA			X	Section 8.1.2.2, Section 8.1.2.3
Photography			X	Section 8.1.4
Assessment of Fingernails Affected by AA			X	Section 8.1.2.4
CGI-AA			X	Section 8.1.2.5
C-SSRS	X	X	X	Section 8.2.9
Patient reported outcomes				
AAPPO			X	Section 8.1.3.1
PGI-C and P-Sat			X	Section 8.1.3.2, Section 8.1.3.3
HADS			X	Section 8.1.3.4

Procedure	Interven	tion Perio	d (Months)	Notes			
Visit	28	32	36				
Observer Reported Outcom	nes		1				
BRIEF®2			X	Only in countries where the BRIEF®2 questionnaire is available and only for participants who are <18 years of age at the time of the Study B7981032 Day 1 visit. The parent/caregiver will complete the questionnaire. For participants who have already started the study when the BRIEF®2 questionnaire is approved and available for use at the participant's site, the BRIEF®2 questionnaire will be administered at the next scheduled study visit and then at the remaining visits per the Schedule of Activities for the BRIEF®2. The BRIEF®2 questionnaire will not be collected for participants who are ≥18 years of age at the time of the visit. Section 8.1.3.9			
Other		•					
Prior and current concomitant medication(s) and treatment(s) monitoring	X	X	X				
Adverse event monitoring	X	X	X				
Contraception check for WOCBP	X	X	X	The contraception check will also be performed monthly between study visits at the time of the phone contact to check the at-home pregnancy test results (see Section 8.2.11 for information on pregnancy testing). Section 5.3.1			
Check for initiation of menarche	X	X	X	For premenarchal females only. Section 8.2.12			

1.3.2.3. Treatment Period 2: Month 40 to Month 60

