8.2.11. Pregnancy Testing

Pregnancy tests are required to be done (if applicable) as specified in the Schedule of Activities.

Pregnancy tests must have a sensitivity of at least 25 mIU/mL. Pregnancy tests should be urine pregnancy tests. In the event that urine pregnancy tests are not permitted at an institution, serum pregnancy tests can be utilized. Pregnancy tests will be performed in WOCBP at the times listed in the Schedule of Activities. Following a negative pregnancy test result at screening, appropriate contraception must be verified and a second negative pregnancy test result will be required at the Day 1 visit prior to the participant receiving the study intervention.

In addition to pregnancy tests performed at the site, site personnel will instruct applicable participants to complete monthly urine pregnancy tests between study visits starting after the Month 1 visit through the Month 60 visit. The pregnancy testing between visits may occur outside of the study site. Urine pregnancy kits will be provided to participants (or their legally authorized representative, if appropriate) at each study visit (starting at Month 1) and site personnel will instruct participants (or their legally authorized representative, if

appropriate) on when and how to administer the pregnancy test and how to interpret the result. The participants (or their legally authorized representative, if appropriate) will be given enough kits to cover the monthly testing between visits (for example, at least 2 kits should be given at the Month 3 visit). Site personnel will be required to document the discussion, including confirmation of participant's willingness to perform the required urine pregnancy tests and understanding of how to perform the test as well as how to interpret the test result. In addition, site personnel will contact participants (or their legally authorized representative, if appropriate) via telephone between study visits to obtain monthly pregnancy test result and ensure that this contact and the result of the pregnancy test are recorded in participant's source documentation and the CRF.

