10.2. Appendix 2: Clinical Laboratory Tests

- The tests detailed in Table 2 will be performed by the central laboratory.
- Local laboratory results are only required in the event that the central laboratory results are not available in time for either study intervention administration and/or response evaluation. If a local sample is required, it is important that the sample for central analysis is obtained at the same time. Additionally, if the local laboratory results are used to make either a study intervention decision or response evaluation, the results must be entered into the CRF.
- Protocol-specific requirements for inclusion or exclusion of participants are detailed in Section 5 of the protocol.
- Additional tests may be performed at any time during the study as determined necessary by the investigator or required by local regulations.
- Pregnancy Testing
 - 1. Refer to Section 5.1 Inclusion Criteria and Section 8.2.11 Pregnancy Testing for screening pregnancy criteria.
 - 2. For details of timing of recommended pregnancy testing see the Schedule of Activities.

Table 2. Protocol-Required Safety Laboratory Assessments

Laboratory Assessments	Parameters					
Hematology	Platelet Count Red blood cell (RB Count Hemoglobin Hematocrit	C)	RBC Indices: MCV MCH Reticulocytes		Count Total Lymp Mono	e blood cell (WBC) with Differential: neutrophils bhocytes cocytes cophils bhils
Clinical Chemistry ¹	Blood urea nitrogen (BUN) Creatinine Glucose Potassium Sodium Calcium Chloride	Aspar Amino (AST) Alanir	tate otransferase ne otransferase	Alkaline phosphatase Direct and Ind bilirubin Total Bilirubin Uric Acid	irect	Total Protein Albumin Creatine Kinase ² Follow-up testing for potential DILI cases ³
Routine Urinalysis ⁴	 pH, glucose, protein, blood, ketones, bilirubin, urobilinogen, nitrite, leukocyte esterase by dipstick Microscopic examination⁵ and urine culture⁶ 					

Table 2. Protocol-Required Safety Laboratory Assessments

Laboratory Assessments	Parameters
Other Screening Tests	 FSH⁷ Pregnancy tests⁸ HIV⁹ HBsAg HBcAb HBsAb¹⁰ HBVDNA¹¹ HCVAb HCVRNA¹² VZV¹³ QFT-G test or T-Spot test¹⁴ Viral Screen¹⁵ Skin biopsies/swabs¹⁶ Fasting Lipid profile¹⁷ The results of each test must be entered into the CRF.

NOTES:

Final

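### The home pregnancy-kit sensitivity in Protocol Section 10.13.3.1 is given as 25 IU/mL, 1000 times laxer than the 25 mIU/mL required by Section 8.2.11

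*Protocol*

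**What the plan says.** Section 8.2.11 of the Protocol states a general requirement: "Pregnancy tests must have a sensitivity of at least 25 mIU/mL".

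Appendix 13 holds the alternative measures for public emergencies. Within it, Section 10.13.3.1 deals with women who need a pregnancy test and cannot visit a local laboratory. For them, and subject to local regulation, "a home urine pregnancy testing kit with a sensitivity of at least 25 IU/mL may be used by the participant". The participant may report the result herself at the remote visit. The same paragraph makes that result a condition of supply: "The urine pregnancy test result must be available prior to dispensing or shipping study intervention to a participant".

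Several cross-references connect the two sections:

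- Section 10.13.3.1 says of its list of laboratory tests, "Refer to the Schedule of Activities for visits at which these tests are required and to Appendix 2 for additional details regarding these tests".
- Appendix 2 says, "Refer to Section 5.1 Inclusion Criteria and Section 8.2.11 Pregnancy Testing for screening pregnancy criteria".
- Sections 10.13.2 (telehealth) and 10.13.5 (home health) both say, "Refer to Section 8.2.11 of the protocol and Section 10.13.3.1 of this appendix regarding pregnancy tests".
- Section 10.13.3.1 adds that monthly testing between visits continues under Section 8.2.11.

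**The concern.** Two sections in force together give different acceptance limits for the same kind of test. As written, the emergency procedure would accept a home kit that needs a concentration 1000 times higher than the main protocol allows before it turns positive. Neither section offers a reason for relaxing the standard at home.

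The sentence sits in a safety step. The home result stands in for site or laboratory testing at a scheduled visit and controls whether drug is released. Section 2.3 reports malformations in animal fetuses, and Section 10.8.2 requires discontinuation on confirmed pregnancy. A site that took the figure literally could rely on a test too insensitive for its purpose. The consequence would be for participant safety only, because nothing in the statistical analysis uses this number.

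**Working it through.** **Inputs**

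| Item | Value | Source |
|---|---|---|
| General requirement for pregnancy tests | 25 mIU/mL | Section 8.2.11 |
| Home kit in a public emergency | 25 IU/mL | Section 10.13.3.1 |

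Each value is a stated specification, so there is no derivation to reproduce. No other numeric sensitivity for a pregnancy test appears in the documents.

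**Conversion**

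1 IU = 1000 mIU, so 25 IU/mL = 25 × 1000 = 25,000 mIU/mL.

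Ratio: 25,000 / 25 = 1000.

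With the unit in Section 10.13.3.1 changed to mIU/mL, both sections read 25 mIU/mL and the ratio is 1.

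**Which figure is intended**

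The number 25 and the way the limit is phrased are the same in both places. Only the unit prefix differs, which fits a dropped m. Section 8.2.11 is worded as a rule for all pregnancy tests, and Section 10.13.3.1 does not say that it replaces that rule. The chain from Section 10.13.3.1 to Appendix 2 to Section 8.2.11 points the same way, though more weakly, because the Appendix 2 link concerns screening criteria.

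**How many drug releases the step can govern**

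Table 5 (Section 10.13.3.1) lists 19 visits, from Week 2 to Month 60. Not all of them release new drug:

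- Week 2 hands back the existing supply: "The Day 1 package will then be returned to the participant for administration and dispensing at the Week 2 visit".
- Month 60 has no dispensing (Section 1.3.2.3).
- At Month 36, "Study intervention will only be dispensed and administered at the Month 36 visit for participants continuing to TP2".

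A participant treated through the whole of Treatment Period 2 has 19 − 2 = 17 visits: Months 1, 3, 6, 9, 12, 15, 18, 21, 24, 28, 32, 36, 40, 44, 48, 52 and 56.

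A participant who stops at Month 36 also loses Months 36, 40, 44, 48, 52 and 56, which leaves 17 − 6 = 11 visits.

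These are ceilings. A visit counts only if Appendix 13 is in force and the woman cannot reach a local laboratory.

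**The case against.** The best case for leaving this as a minor editorial matter is that Section 8.2.11 already binds every pregnancy test and a kit that meets it meets both sections. Section 8.2.11 also has sites give participants kits at each visit from Month 1 and instruct them in their use, so a participant is less likely to choose her own kit. Other safeguards do not depend on this figure: serum testing after an ambiguous urine result, testing after a missed cycle, contraception checks at remote visits, and the highly effective contraception required throughout. All of this stands, and it is why the practical risk is small. It does not make the figure right. The supplied kits are described for testing between visits, and Section 10.13.3.1 does not say who provides the kit for a remote scheduled visit. Sections 10.13.2 and 10.13.5 send the reader to both sections without ranking them.

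The visit count can also be challenged. The release condition covers dispensing or shipping, and the Schedule of Activities marks Week 2 as a dispensing visit. Counting Week 2 gives 18 and 12 in place of 17 and 11. Section 10.13.1 also allows a home test at Day 1 for participants who roll over from B7981015 within 30 days, and Day 1 lies outside Table 5. The counts of 17 and 11 are correct for Table 5 visits that release new drug. The broader counts do not change the conclusion.

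Finally, a letter lost when the PDF was converted to text cannot be fully excluded. The surrounding text reads cleanly, and a glance at the issued PDF settles the point.

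**Conclusion.** The inconsistency is real. Section 10.13.3.1 states a limit of 25,000 mIU/mL against 25 mIU/mL in Section 8.2.11, and no passage supports the difference. It is best described as a unit error in a safety procedure. It should be corrected because the affected test must be completed before a drug with fetal findings in animals is supplied.

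The conclusion assumes that both sections mean a kit able to detect at the stated concentration or lower, and that the issued PDF reads as quoted. The dropped m is an inference, though a well-supported one. How many women were or could be affected is not given, and the documents contain no sign that an inadequate kit was supplied or used.

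**What to change.** In Section 10.13.3.1, change IU/mL to mIU/mL. Alternatively, delete the figure and refer to Section 8.2.11, which leaves a single source for the requirement. Either change can go into the next amendment or an administrative letter. A separate notice to sites is optional, because Section 8.2.11 already imposes the correct limit. The cost is one unit of text, with no effect on data collection, sample size or analysis.
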